I will provide copies of the protocol and all pertinent information to all individuals responsible to me who assist in the conduct of this study. I will discuss this material with them to ensure that they are fully informed regarding the study treatment, the conduct of the study, and the obligations of confidentiality.

This document is signed electronically through submission and approval by the Principal Investigator at Huntsman Cancer Institute in the University of Utah IRB Electronic Research Integrity and Compliance Administration (ERICA) system. For this reason, the Principal Investigator at Huntsman Cancer Institute will not have a hand-written signature on this signature page.

Instructions to multi-site Principal Investigators at locations other than Huntsman Cancer Institute: SIGN and DATE this signature page and PRINT your name. Return the original, completed and signed, to the HCI Research Compliance Office. Retain a copy in the regulatory binder.

Signature of Principal Investigator

Date

Principal Investigator Name (Print)

Name of Institution

STUDY SUMMARY

Title	Cabozantinib plus pembrolizumab as first-line therapy for cisplatin-ineligible advanced urothelial carcinoma
Short Title	CaboPembro UC
Protocol Number	IRB#104688
IND	IND#139643
Phase	Phase II
Design	Single-arm, nonrandomized phase II study to test efficacy of combination pembrolizumab and cabozantinib.
Study Duration	Accrual will take approximately 1-2 years with 1 year of treatment and 6 months follow up. Total study duration 3-4 years.
Study Centers	This study will be conducted at the Huntsman Cancer Institute and up to two additional cancer centers.
Objectives	Primary Objective: Evaluate measurable disease overall response rate (ORR). Secondary Objectives: Evaluation of progression-free survival (PFS) at 6 months (PFS6), overall survival (OS), and evaluation of toxicities of the combination.
Number of Subjects	39 subjects will be enrolled to ensure 35 evaluable patients
Diagnosis and Main Eligibility Criteria	
Cisplatin-ineligible urothelial carcinoma
 
Key Inclusion Criteria:
 
• Histologically proven transitional cell or urothelial carcinoma (UC).• Metastatic (any N+ or M1) or locally advanced, unresectable (T4bN0) disease.• Measurable disease is required as determined by RECIST v1.1.• Cisplatin-ineligibility based on ≥ 1 of the following:
○ Estimated CrCl of between ≥ 40 and < 60 ml/min (CG formula)○ ECOG PS ≥ 2○ Hearing loss○ Baseline neuropathy○ Patient refusal 
Key Exclusion Criteria:
 
• Prior chemotherapy for metastatic/ advanced urothelial carcinoma.• Prior chemotherapy treatment for localized urothelial carcinoma that has been completed less than 6 months before registration.

	
• Small-cell or sarcomatoid component in histology.
Study Product, Dose, Route, Regimen	Pembrolizumab 200mg IV q 3 weeks with cabozantinib administered 40mg orally, with dose reductions to 20 mg daily. Subsequent dose reduction to 20 mg every other day to improve tolerability is allowed.
Duration of administration	Patients will receive therapy until treatment discontinuation criteria is met or until 12 months from start of therapy
Reference therapy	Study treatment will be compared to pembrolizumab as single agent.
Statistical Methodology	A 95% one-sided exact binomial confidence interval (Clopper-Pearson) will be calculated for ORR. With 35 evaluable subjects the lower bound of the 95% confidence interval will extend no more than 26% from the observed proportion. If there are 17 or more objective responses in 35 patients the confidence interval will exclude 32%. Secondary analyses will include an association of risk group (based on performance status and visceral metastasis) with PFS. Stratified Kaplan-Meier methodology will be used to associate risk group (based on performance status and visceral metastasis) with PFS.

1 OBJECTIVES

1.1 Primary Objective and Endpoint

To evaluate measurable disease overall response rate (ORR).

Endpoint: Subjects will be evaluated by CT scans at regular intervals for disease assessment by RECISTv1.1 criteria for the duration of treatment.

1.2 Secondary Objectives and Endpoints

1.2.1 To evaluate progression-free survival (PFS) at 6 months (PFS6).

Endpoint: Subjects will be evaluated by CT scans at regular intervals for disease assessment by RECISTv1.1 criteria for the duration of treatment.

1.2.2 To evaluate Overall Survival (OS).

Endpoint: Subjects will be evaluated using Kaplan-Meier estimation for survival for up to 6 months after discontinuation of study treatment; patients surviving longer than 6 months will be censored.

1.2.3 To evaluate toxicities associate with the combination treatment.

Endpoint: Adverse events will be collected beginning with study treatment and tabulated according to drug attribution.

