4 STUDY DESIGN

4.1 Description

This is an open label, non-randomized phase 2 study of the combination of pembrolizumab and cabozantinib to assess overall response rate (ORR), progression free survival at 6 months (PFS6), and overall survival (OS) in patients with metastatic urothelial carcinoma (UC) ineligible for cisplatin. Cabozantinib is administered at 40 mg oral daily. Pembrolizumab will be administered at a fixed dose of 200mg intravenously every 3 weeks for all patients. A safety analysis will be performed after the first 6 patients enroll and receive treatment.

During this stage, the decision to continue enrollment will be made by the Data Safety and Monitoring Committee (DSMC). When all 6 subjects in the have been followed for at least 21 days following first dose of pembrolizumab and cabozantinib, all available safety data will be considered in a decision to continue enrollment. Therapy continues until progression or intolerable toxicities. Study treatment may continue beyond initial radiographic or clinical disease progression as long as the patient is deriving clinical benefit from the treatment, as assessed by the investigator. Patients removed from therapy without evidence of progression will undergo radiological examination every 12 weeks or earlier if clinically warranted.

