6.9 Duration of Therapy

Subjects enrolled after Amendment 7 (version date 08NOV2021) will remain on study treatment for up to 12 months. After consultation with PI, subjects enrolled prior to Amendment 7 (version date 08NOV2021) who have demonstrated a response to study treatment may continue beyond 12 months of treatment, if there is demonstrated continued clinical benefit.

Study treatment may continue beyond initial radiographic or clinical disease progression for up to 12 months as long as the patient is deriving clinical benefit from the treatment, as assessed by the investigator.

Subjects must be withdrawn from the study treatment for the following reasons:

- Subject withdraws consent from the study treatment and/or study procedures. A subject must be removed from the trial at his/her own request or at the request of his/her legally acceptable representative. At any time during the trial and without giving reasons, a subject may decline to participate further. The subject will not suffer any disadvantage as a result.
- Radiographic disease progression by RECIST v1.1 (progression must be confirmed with follow up scan no less than 4 weeks and no more than 8 weeks after the first scan shows disease progression). Study treatment may continue beyond initial radiographic disease progression as long as the patient is deriving clinical benefit from the treatment, as assessed by the investigator.
- Progressive disease (PD), without clinical benefit, as determined by the investigator.
- Specific conditions described in the Management of Adverse Events Section 7.
- An AE or intercurrent illness that in the opinion of the investigator warrants the subject's withdrawal from study treatment.
- Subject is lost to follow-up.
- Necessity for treatment with other treatment prohibited by protocol.
- Sexually active subjects who refuse to use medically accepted barrier methods of contraception (e.g., male condom, female condom) during the course of the study and for 120 days after discontinuation of study treatment.
- Women who become pregnant or are breastfeeding.
- If the subject does not recover from his or her toxicities to tolerable Grade ≤ 2 within 6 weeks, the subject will have study treatment discontinued unless there is unequivocal evidence that the subject is benefitting. In this situation, a subject may be able to restart therapy with a dose reduction upon resolution of the toxicity.

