21. Follow up visits: Patients will be followed via telephone contact or medical record review for survival 6 months after completing study treatment. Patients removed from therapy without evidence of progression will undergo radiological examination every 12 (± 1) weeks or earlier, if clinically warranted.
22. B type Natriuretic Peptide should be collected
23. Pre-screening ICF and eligibility review must be completed with 4 weeks prior to urothelial carcinoma diagnostic procedure (soft tissue biopsy or TURBT).

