9.5 Follow-up Assessments

Patients will be followed for 6 months after cessation of study treatment for survival.

Patients removed from therapy without evidence of progression will undergo radiological examination every 12 weeks or earlier, if clinically warranted.

Patients will be followed for SAEs for 90 days after the cessation of treatment

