11.2 Secondary Objectives and Endpoints

The secondary objectives are to evaluate progression free survival at 6 months and overall survival of pembrolizumab + cabozantinib in subjects with UC. Kaplan-Meier methods and associated confidence intervals will be used to analyze PFS and OS. Subjects will be evaluated for survival for 6 months or until death after discontinuation of study treatment. The proportion of subjects who exhibit an objective response will be reported along with an exact binomial confidence interval. As an additional secondary analysis, stratified Kaplan-Meier methodology will be used to associate risk group (based on performance status and visceral metastasis) with PFS.

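### OS is censored 6 months after each patient's own treatment stop, so the Kaplan-Meier curve beyond month 6 carries dependent censoring whose direction the OS data as defined cannot show

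*Combined protocol and SAP*

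**What the plan says.** Section 1.2.2 defines OS by Kaplan-Meier estimation "for survival for up to 6 months after discontinuation of study treatment; patients surviving longer than 6 months will be censored". Three other places give the same window:

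- Section 8, footnote 21: "Patients will be followed via telephone contact or medical record review for survival 6 months after completing study treatment".
- Section 9.5: "Patients will be followed for 6 months after cessation of study treatment for survival".
- Section 11.2: "Subjects will be evaluated for survival for 6 months or until death after discontinuation of study treatment".

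The Study Summary also gives 6 months. Section 4.4 gives 5 months, an inconsistency that does not alter this point.

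The estimator in Section 11.2 is unadjusted: "Kaplan-Meier methods and associated confidence intervals will be used to analyze PFS and OS". No common data cutoff, sensitivity analysis, OS time origin or OS landmark is stated.

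Stopping is tied to the course of disease. Section 4.1 has "Therapy continues until progression or intolerable toxicities", with continuation past first progression allowed while the patient benefits. The stopping reasons in Section 6.9 include adverse events, intercurrent illness and "Progressive disease (PD), without clinical benefit, as determined by the investigator". Section 6.9 also caps treatment at 12 months, except that subjects enrolled before Amendment 7 "who have demonstrated a response to study treatment may continue beyond 12 months of treatment, if there is demonstrated continued clinical benefit".

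**The concern.** Kaplan-Meier needs patients censored at a given time to have the same later death hazard as those still at risk. Here the censoring time is the patient's own stop time plus 6 months, so early stoppers leave the risk set first. At month 12 the risk set holds only patients still on treatment at month 6 or later. At month 17 it holds only those still on treatment at month 11 or later. Patients who come off early because the disease progressed are unlikely to share the prognosis of patients treated for most of a year, and the plan neither assumes nor tests that they do.

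OS is a named secondary endpoint. If a later survival rate or a median is read off this curve, it can be off systematically, and the Kaplan-Meier confidence interval will not show it. Survival status that was never collected cannot be recovered by later analysis.

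**Working it through.** **Plan figure to reproduce.** There is none for OS: the documents give no target, event count, landmark or hazard. Every hazard below is an assumption.

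**Step 1, structure.** Let S be the stop time and C = S + 6 the censoring time, both in months from first dose. Since S is at least 0, C is at least 6, so the rule censors nobody before month 6. For t > 6, let w be the share of patients alive at t who are already censored. Then

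- true hazard at t = w × h(censored) + (1 − w) × h(at risk)
- Kaplan-Meier hazard at t = h(at risk)
- difference (Kaplan-Meier minus true) = w × [h(at risk) − h(censored)].

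Kaplan-Meier is pushed too high when censored patients die faster than those at risk, and too low when they die more slowly. h(censored) is the hazard more than 6 months after stopping, which the OS data exclude.

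**Step 2, one observed data set, several truths.** Inputs:

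- Median time to stop 4.8 months, a proxy from the first chemotherapy PFS median in Section 11.1; 12-month cap.
- Assumed: 20% of earlier stops are not for progression.
- Assumed death hazard: 0.01/month on treatment; 0.10/month in the first 6 months after a progression stop, and half that after other stops.
- Beyond 6 months after stopping, the hazard is m times its early level. The OS rule never observes m.

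Without deaths on treatment, the share stopping by month 6 is 1 − 0.5^(6/4.8) = 58%. Simulation gives 33.2% censored alive by month 12, or 0.332 × 39 ≈ 13 patients.

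| m | Kaplan-Meier, month 12 | True OS, month 12 | Difference (points, rounded values) |
|---|---|---|---|
| 0.25 | 60.2% | 63.1% | −2.9 |
| 1 | 60.2% | 57.1% | +3.1 |
| 2 | 60.2% | 51.5% | +8.7 |

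The Kaplan-Meier value is the same in every row because the observed data are the same. Without any assumption on m, the data bound 12-month OS only between 32.3% (all censored patients dead by month 12) and 32.3 + 33.2 = 65.5% (all alive). The sign changes at m = 0.57 here, and at 0.39 to 0.67 across the scenarios run.

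**Step 3, wider scenarios.** Stop medians of 4.8 and 7.6 months (both from Section 11.1), 12-month cap:

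| Assumed post-stop hazard | Month 12 (points) | Month 17, completers take post-stop hazard | Month 17, completers keep on-treatment hazard |
|---|---|---|---|
| Constant, above on-treatment (post-stop median 6, 8 or 12 months; on-treatment death 1, 3 or 4%/month) | +0.7 to +3.6 | +0.6 to +2.1 | +2.1 to +9.6 |
| Falling after 6 months, still above on-treatment | −0.1 to −2.9 | −3.5 to −9.2 | −4.0 to +1.0 |

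With equal hazards (6%/month throughout) the difference is within 0.1 point. At month 6 it is zero in every scenario. Across the constant and falling scenarios the median shifts by about −0.5 to +2.7 months. Of 39 patients, about 7 to 17 are at risk at month 12 and 2 to 12 at month 17. Letting half of the completers continue for a mean of 6 more months, as a check on the pre-Amendment 7 exception, leaves month 12 essentially unchanged.

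**Step 4, against sampling error.** The simulated standard error of 12-month Kaplan-Meier OS at n = 39 under this censoring is 7.8 to 9.7 points. The 95% half-width is therefore 1.96 × 7.8 = 15.3 to 1.96 × 9.7 = 19.0 points.

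**The case against.** Several objections have force.

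- **Some later vital status will exist.** Sections 4.1, 6.1 and 9.5 and footnote 21 require scans about every 12 weeks, with no end date, for patients removed without progression. Section 15.4.2 requires late deaths to be reported if thought treatment-related. A reader might infer that nobody is seen beyond 6 months after stopping, and the documents do not support that. But the scans leave out patients who stopped for progression, the late-death rule is selective, and Section 1.2.2 censors at 6 months regardless.
- **The time origin is undefined.** If OS ran from discontinuation, everyone would be censored at the same 6 months and the problem would disappear. First dose is the usual reading for OS, but it is an assumption here.
- **No landmark is planned.** The 12-month rate and the median are natural summaries of the curve, not commitments in Section 11.2.
- **The practical effect is modest.** OS carries no hypothesis or decision, and the month-12 differences computed lie inside the sampling error. This stands and limits the weight of the point. It does not remove it, since a confidence interval conveys sampling error and not this bias.

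The tempting stronger reading is that OS will be overstated. The documents do not establish that. Upward bias follows if the post-stop hazard stays constant or rises, but nothing in the OS data as defined can confirm either. Nor are the two directions evenly balanced: deaths clustering soon after stopping do not by themselves reverse the sign. With 1%/month on treatment, a 4.8-month stop median and 10%/month early after stopping, a later fall to 8% or 7% still leaves Kaplan-Meier 2.0 or 1.2 points too high at month 12.

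**Conclusion.** The concern holds in limited form. With OS measured from first dose, the follow-up rule leaves the curve unbiased by that rule through month 6 and subject to dependent censoring afterwards. Withdrawal or loss to follow-up could still censor earlier.

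At month 12 the assumed hazards give about 1 to 4 points too high (constant, raised post-stop hazard), about 9 too high (hazard doubling after 6 months), or up to about 3 too low. The last needs the later hazard to fall below roughly 0.4 to 0.7 of its early level. Later points can be further off in either direction, on few patients. These sizes rest on stop times borrowed from chemotherapy PFS and on hazards the documents do not supply, so they illustrate and do not predict. The sign is not identified from OS as defined.

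ORR and its interval are untouched. The change is worth making because the missing follow-up must be planned before it is lost.

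**What to change.** In Sections 1.2.2, 9.5 and 11.2 and footnote 21 of Section 8, define OS from first dose. Follow every patient for survival, by the telephone contact or record review already planned, to one study-wide cutoff that does not depend on treatment status. Censor at that cutoff or at the last date known alive. One workable choice is 18 months after the last patient's C1D1. With the 24 months of accrual allowed in Section 4.4, that is month 24 + 18 = 42, or 3.5 years, within the stated 3 to 4 years. In simulation this cutoff brought the difference to 0.0 at months 6, 12 and 17. Align the follow-up lengths in Section 4.4 and the Study Summary at the same time.

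The cost is a protocol amendment, with the approvals in Section 15.8, and longer telephone or record follow-up. The longest extension is for early enrollees: a first-enrolled patient who stops at month 3 is now followed to month 9 and would be followed to month 42, which is 33 months more.

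If follow-up is not extended, report 6-month OS from first dose as the landmark that the rule does not affect. Label later rates, and a median reached after month 6, as subject to dependent censoring of unknown direction. That needs wording only.

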1.3 Exploratory Objectives and Endpoints

1.3.1 To evaluate molecular markers for pharmacodynamic pathways associated with response.

Endpoints: Blood, tissue, and stool samples will be collected at various time points to measure molecular markers to correlate with response to develop a panel predictive of response which will be validated in future studies. Once the model is determined, statistical methods will be determined.

1.3.2 To evaluate ORR and PFS6 using immune specific disease assessment criteria

Endpoint: Subjects will be evaluated by CT scans at regular intervals for disease assessment by iRECIST criteria for the duration of treatment.

2 BACKGROUND

Currently the standard of care first-line therapy for urothelial carcinoma (UC) is cisplatin based chemotherapy. However, many patients diagnosed with UC are not eligible for cisplatin due to age, frailty or other comorbid conditions. In a retrospective analysis of 299 patients presenting in a community-based cancer center system with stage 4 disease, the regimens administered were cisplatin based in 107 patients (35.9%), carboplatin based in 81 (27.2%), and non-platinum based in 25 (8.4%).¹ Notably, no chemotherapy was administered in 71 (23.8%) patients. Cisplatin administration was more common in patients aged \leq 70 years (62/150 [41.3%]) as opposed to $>$ 70 years (45/148 [30.4%]) ($P = 0.05$).

In another retrospective study of 1031 patients aged ≥ 66 years presenting with advanced bladder cancer in the SEER-Medicare linked database, among patients receiving chemotherapy, carboplatin accounted for 50.6%, cisplatin for 39.7% and other agents for 9.8%.² A relatively large proportion of patients did not receive chemotherapy in this Medicare database (48.4%), again highlighting the difficulties of administering aggressive chemotherapy in this population. The reasons for non-administration of cisplatin were not available in both of these studies, although it may be postulated that the presence of renal dysfunction, poor performance status, elderly age and comorbidities likely are responsible as these are frequent exclusion criteria for previously reported large phase III clinical trials of cisplatin based chemotherapy for UC.

Carboplatin is often substituted for cisplatin in cisplatin-ineligible patients, but is associated with inferior response rates, especially CR rates, which suggests the lack of potential cures. In a meta-analysis of randomized phase II trials, cisplatin-based chemotherapy was associated with a significantly higher likelihood of achieving a CR (relative risk {RR} = 3.54; 95% confidence interval {CI} 1.48-8.49; P = 0.005) and ORR (RR = 1.34; 95% CI 1.04-1.71; P = 0.02) compared to carboplatin-based chemotherapy.³ Clearly, other tolerable and high-effective therapies are needed for this population of patients with cisplatin-ineligible invasive urothelial carcinoma.

In a previously reported study,⁴ prognostic markers for poor clinical outcomes associated with disease progression were studied. The authors demonstrated that expression of Met was positively associated with histologic grade, stage classification, tumor size, and nodular tumor growth (P < .05, respectively) in urothelial carcinoma. Factors that predicted disease progression were tumor stage, Met status, and TP53 accumulation (P < .05, respectively). Indicators for poor long-term survival were invasive cancer, multiple tumors, and Met overexpression (P = 0.0006, 0.01 and 0.04, respectively). The authors concluded that the c-met proto-oncogene plays a more important role in the progression of bladder carcinogenesis. Evaluation of Met expression could identify a subset of bladder cancer patients who may benefit from molecularly targeted therapy.

In a recent report, a positive association of Axl or platelet-derived growth factor receptor-alpha (PDGFR- α) with c-Met expression was demonstrated through preclinical models of disease.⁵ The transactivation of c-Met on Axl or PDGFR- α in vitro was through a ras- and Src-independent activation of mitogen-activated protein kinase/extracellular signal-regulated kinase (MEK/ERK) pathway. In human bladder cancer, co-expression of these RTKs was associated with poor patient survival (p < 0.05), and overexpression of c-Met/Axl/PDGFR- α or c-Met alone showed the most significant correlation with poor survival (p < 0.01). Thus, in addition to c-Met, the cross-talk with Axl and/or PDGFR- α also contributes to the progression of human bladder cancer.

Finally, recent data⁶ suggest significant activity for Met inhibition in bladder cancer. PF-2341066 (crizotinib), a small, orally available, highly specific Met-inhibitor was evaluated in an orthotopic xenograft model of bladder transitional cell carcinoma (TCC). Animals were treated with intra peritoneal PF-2341066 after positive detection of bladder tumor primary and/or metastatic disease. Fluorescence imaging (Xenogen IVIS) of mice was performed weekly. Mice were euthanized 4 weeks after the start of treatment and their tissues studied histologically. PF-2341066 was found to reduce tumor burden to below detectable levels in both primary and metastatic sites in all mice treated. No noticeable side effects were detected in treated mice secondary to drug administration. Thus, this was the first study to test a small orally available

Met-selective inhibitor in an orthotopic, HGF-driven model of human bladder cancer, supporting its potential use in patients with bladder cancer.

In vitro biochemical and/or cellular assays have shown that cabozantinib inhibits the tyrosine kinase activity of RET, MET, VEGFR-1, -2 and -3, KIT, TRKB, FLT-3, AXL, and TIE-2. This suggests that cabozantinib may be effective in urothelial carcinoma. This concept is currently being studied in an ongoing clinical trial evaluating the efficacy of single agent cabozantinib (NCT01688999), with final results expected soon. Preliminary results suggest clinical activity with single agent cabozantinib with objective radiographic responses seen.

Previously, immune-based treatments have demonstrated significant clinical benefit as single agent therapies in UC. To date, many different immunotherapies are approved with PD-1 antagonists (pembrolizumab, nivolumab) and PD-L1 antagonists (atezolizumab, avelumab, durvalumab). In the second-line pembrolizumab trial for patients with UC (KEYNOTE-045)⁷, 542 patients were randomized to pembrolizumab or the treating physician's choice of chemotherapy (vinflunine, docetaxel or paclitaxel) with significant clinical benefit demonstrated in the pembrolizumab arm. The overall survival was improved at 10.3 months versus 7.4 months for pembrolizumab versus chemotherapy respectively (HR for death 0.73; 95% CI 0.59—0.91; P = 0.002). It was also better tolerated with decreased grade 3-5 adverse events (15.0% versus 49.4% respectively). Pembrolizumab is now one standard-of-care option that is FDA approved for UC in the second-line setting. Similarly, durvalumab⁸, atezolizumab,⁹ and nivolumab¹⁰ have also demonstrated efficacy in the second-line setting, while pembrolizumab¹¹ and atezolizumab¹² have demonstrated efficacy in the first-line setting. Immunotherapy for urothelial carcinoma is clearly effective, active therapy in urothelial carcinoma. However, the primary challenge with these therapies is the relatively low response rate. In the KEYNOTE-045 clinical trial of second-line pembrolizumab for instance, there was a low 21.1% response rate for pembrolizumab compared to 11.4% with chemotherapy. Robust responses are frequently observed with immunotherapy, but unfortunately only a relatively few number of patients experience a response to this type of treatment.

Using both cabozantinib plus pembrolizumab in cisplatin-ineligible UC is attractive as this may be a well-tolerated and synergistically active combination. VEGFR therapy appears to modulate the immune system, suggesting possible clinical benefit for this combination. In mouse models, axitinib (another multi-targeted kinase inhibitor similar to cabozantinib) demonstrated a significant increase in the number of tumor infiltrating lymphocytes and altered the microenvironment from a suppressive to a stimulatory environment relative to vehicle controls.¹³ Another study analyzing archival tissue from patients with metastatic renal cell carcinoma demonstrated a positive relationship between tumor-infiltrating lymphocytes and VEGF gene expression ($r = -0.18$; $P = 0.089$), suggesting that the VEGF pathway partially regulates the immune effect in kidney cancer. This theory has been tested in a pilot clinical trial of ten patients.¹⁴ Patients were treated with 1 cycle of bevacizumab (a VEGF antagonist) prior to treatment with the combination of atezolizumab (a PD-L1 antagonist) and bevacizumab. Patients underwent biopsies at baseline, after the lead-in phase with bevacizumab and after two cycles of the combination therapy. The tumor tissue demonstrated an increase in gene signatures associated with Th1, CD8, and natural killer cell activity after treatment at all times in the study including after the bevacizumab-only period. This strongly suggests that the combination of VEGFR TKI and immunotherapy with PD-L1 therapy will be effective and safe in patients with

metastatic urothelial carcinoma. Perhaps most importantly, the combination of axitinib plus avelumab was recently reported in a phase IB clinical trial of 55 patients with metastatic renal cancer.¹⁵ This combination appears to be relatively well tolerated with an incidence of grade 3-5 toxicities in 52% (axitinib related) and 20.0% (avelumab related) of patients. The confirmed overall response rate was 54.5% (95% CI 40.6—68.0) with 2 complete responses and 28 partial responses. Though this trial is in a different disease state than the proposed clinical trial, this combination of a VEGF targeted therapy plus a PD-1 antagonist appears to be safe and well tolerated, and potentially more active than single agent immunotherapy.

We hypothesize that the combination of cabozantinib plus pembrolizumab will be safe in cisplatin-ineligible patients as a first-line treatment. Also we hypothesize that this combination will demonstrate significant additive or synergistic activity resulting in a 20% increase in response in this disease compared to historic benchmarks for progression-free survival.

